6.2 Secondary Objective(s)

- Describe the incidence of gastroesophageal symptoms, injury, or complications: defined as the rate of patient-reported gastroesophageal symptoms (e.g. painful or difficulty swallowing, hoarseness, or eating), swallowing dysfunction (defined by the need for a postoperative swallowing evaluation after surgery), or diagnosis of a new gastroesophageal problem (defined by the need for an upper endoscopy after surgery).

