8.5.2 Survey Data Collection

- The PI ([name]) or other IRB-approved research personnel will conduct two interviews with the patient: (1) the first interview will occur following extubation (i.e. removal of the breathing tube after CABG surgery) within a 6 – 24 hour post-surgical window; (2) the second interview will occur at any point between 1 – 5 days post-surgery. These interviews will take approximately 15 – 30 minutes.

Clinical Study Number:	NCT06154265	Document Title:	10/24/2024	Page 16 of 36
		Default vs As-Needed Intraoperative Transesophageal Echocardiography (TEE) in Low-Risk Isolated Coronary Artery Bypass Graft (CABG) Surgery: A Randomized Controlled Trial		

- No identifying information from the patient will be collected. Survey data will be labeled only by subject number.
- Patient Interview Questions
 - 1. Did you, or do you currently have symptoms of throat soreness?
 - 2. Does your throat feel dry or scratchy?
 - 3. Have you had difficulty swallowing liquids, pills, or food?
 - 4. Has swallowing been painful?
 - 5. Have you felt nauseous or vomited?
 - 6. Have you had symptoms of acid reflux?
 - 7. Did you ever have the taste of blood in your mouth?
 - 8. Have you had any GI symptoms I haven't asked you about?

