19.2.2 RCT Retention Plan

- To ensure optimal retention of RCT participants, we will follow an enhanced retention approach that includes collecting contact information (e.g. physical address, mobile phone numbers, email address, etc.) from each participant. We will also ask the participant to designate one other individual to allow researchers to locate and communicate with participants in the event that the participant cannot be reached directly.
- During the trial, the RCT protocol will involve a member of the research team conducting in-person interviews post-CABG surgery with each study participant. Interview questions will cover incidence of clinical adverse sequelae (e.g. difficulty or painful swallowing, hoarseness, etc.) in each trial arm and will also involve asking open-ended questions regarding the study protocol to allow participants to provide feedback to research team personnel on how to optimize the study protocol for participating subjects. We will encourage study participants to consider themselves essential members of the study team with valuable information that is critical to the success of a future trial. At the end of the study, we will invite patients to consider staying on as representative stakeholders to serve on a monitoring board for a future, multicenter RCT comparing default vs as-needed intraoperative TEE during isolated CABG surgery.
- During the course of the study, we will encourage patients to directly contact research team personnel or the PI ([name]) at any point before, during, or following RCT completion. To facilitate this level of open communication, participating RCT subjects will be provided the PI ([name]'s) mobile phone number in the information packet. Subjects will be told they can contact the PI directly 24/7 to answer questions or address concerns regarding RCT participation.

Clinical Study Number:	NCT06154265	Document Title:	10/24/2024	Page 34 of 36
		Default vs As-Needed Intraoperative Transesophageal Echocardiography (TEE) in Low-Risk Isolated Coronary Artery Bypass Graft (CABG) Surgery: A Randomized Controlled Trial		

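### Hoarseness is named as a gastroesophageal symptom in 6.2 and promised as interview content in 19.2.2, but none of the eight questions in 8.5.2 directly asks about voice

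*Combined protocol and SAP*

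**What the plan says.** Three places bear on this.

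- **Section 6.2, Secondary Objective(s)**, defines the gastroesophageal outcome through three routes: patient report, need for a swallowing evaluation, or need for an upper endoscopy. The patient-report route is the rate of "patient-reported gastroesophageal symptoms (e.g. painful or difficulty swallowing, hoarseness, or eating").
- **Section 19.2.2, RCT Retention Plan**, describes the interview that supplies the patient report: "Interview questions will cover incidence of clinical adverse sequelae (e.g. difficulty or painful swallowing, hoarseness, etc.) in each trial arm".
- **Section 8.5.2, Survey Data Collection**, lists eight questions under a heading for patient interview questions. The first interview falls 6 to 24 hours after surgery, once the patient is extubated. The second falls 1 to 5 days after surgery.

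The Synopsis and section 10.2 restate the outcome as clinically significant dysfunction, shown by patient-reported symptoms or by testing. Neither lists the symptoms. Section 10.2 adds that the clinical data are meant to help plan a later, powered trial.

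**The concern.** The outcome definition and the instrument that feeds it should name the same symptoms. Here the definition names hoarseness, the appendix says the interview covers it, and the question list has no item for it. A symptom that is not asked about tends to be reported less often than one that is. The hoarseness component then depends on what patients happen to mention and staff happen to write down, while the other named symptoms are asked of everyone.

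What is at stake is the completeness of a descriptive rate to be carried into the design of the next trial. The interviews finish by day 5, so a patient report not obtained then cannot be reliably recovered later.

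**Working it through.** The plan gives no figure on this point and no formula applies. The check is an item-by-item comparison of the questions in 8.5.2 with the symptoms named in 6.2 and 19.2.2.

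**The eight questions**

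| No. | Question in 8.5.2 | Asks about voice? |
|---|---|---|
| 1 | "Did you, or do you currently have symptoms of throat soreness" | No: throat pain |
| 2 | "Does your throat feel dry or scratchy" | No: throat sensation |
| 3 | "Have you had difficulty swallowing liquids, pills, or food" | No: swallowing |
| 4 | "Has swallowing been painful" | No: swallowing |
| 5 | "Have you felt nauseous or vomited" | No |
| 6 | "Have you had symptoms of acid reflux" | No |
| 7 | Taste of blood in the mouth | No |
| 8 | Any other GI symptom not yet asked about | Not named; limited to GI symptoms |

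Questions that ask about voice: 0 of 8.

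**The named symptoms, traced to a question**

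| Symptom | Named in 6.2 | Named in 19.2.2 | Matching question |
|---|---|---|---|
| Painful swallowing | Yes | Yes | 4 |
| Difficulty swallowing | Yes | Yes | 3 |
| Difficulty eating | Yes | No | 3, in part (food) |
| Hoarseness | Yes | Yes | None |

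Hoarseness is the only named symptom without a question.

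**Other routes by which it could be recorded**

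1. Question 8. A patient need not think of a hoarse voice as a GI symptom, so this is a weak prompt.
2. The open-ended questions in 19.2.2. These ask for feedback on the study protocol, not for symptoms.
3. Medical record review to day 5 (8.5.1). This finds hoarseness only if a clinician charted it, and it is not a patient report.
4. Adverse event recording (13.1). The general definition in 19.1.1.1 is wide enough to include hoarseness. The itemized list there does not name it; the nearest entries are a gastrointestinal or esophageal complication that needs diagnostic testing, and a failed swallow evaluation.

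Each route is possible, but none puts the same question to every patient.

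**The case against.** The strongest case on the other side has four parts.

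*Hoarseness is only an example.* In both 6.2 and 19.2.2 it follows an e.g., and the Synopsis and 10.2 do not mention it. This stands to the extent that hoarseness cannot be called a required component, and the documents do not say whether hoarseness alone would count as clinically significant. It does not answer 19.2.2, which says the questions will cover it.

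*It may still be captured.* A reader might infer that hoarseness is never elicited at all. The documents do not support that. Section 8.5.2 does not say its list is verbatim or exhaustive, an interviewer could record hoarseness under question 8 because 6.2 itself classes it as gastroesophageal, and record review and adverse event logging remain. The supportable statement is that it is not directly asked.

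*The list also departs from 6.2 in the other direction.* A reader might object that nausea and vomiting are asked about although 6.2 does not name them. Because the list in 6.2 is illustrative, asking about more symptoms contradicts nothing. Throat soreness, dry throat, reflux and taste of blood are in the same position. No fault lies there.

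*The outcome is secondary and both arms get the same questions.* This is correct, and it limits the importance of the point. It does not make the rate complete. Every patient is intubated before randomization (8.4.1), so any hoarseness unrelated to the probe could occur in both arms. Describing the arms side by side is then informative only if the symptom is sought the same way in each.

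**Conclusion.** The mismatch is real and can be seen by reading the three sections together: hoarseness is named twice and directly asked about in none of the eight questions. The likely consequence is under-ascertainment of one symptom within a descriptive secondary outcome. That conclusion rests on one assumption, that unprompted reporting and charting find fewer cases than a direct question.

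The size cannot be given. A reader might be tempted to estimate how many patients would be missed, but the documents supply no rate of hoarseness and nothing on how often it occurs without a sore throat or another symptom that is asked about. If hoarse patients usually report one of those as well, they already count as symptomatic and few would be lost from the overall symptom rate; the rate of hoarseness itself would still be incomplete. The denominator is also unsettled: section 10.3 gives 22 per arm, while 19.5.2 gives 22 as the projected trial enrollment, which would be 11 per arm under equal allocation.

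Neither primary endpoint (recruitment, and TEE use in the as-needed arm) depends on the interview, and the sample size was not derived from this outcome. This is a small defect, worth correcting because the correction is nearly free.

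**What to change.** Add one question to 8.5.2, asked at both interviews in both arms, for example: *Since your operation, has your voice been hoarse or changed?* Add the matching CRF field. In 6.2 or 10.2, state which question responses count toward the patient-reported symptom rate, including whether hoarseness alone is enough.

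Deleting hoarseness from 6.2 and 19.2.2 would also make the sections agree, but it gives up a symptom that the plan names in two places.

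The cost is one more question within interviews already planned at 15 to 30 minutes, one data field and a minor amendment. No visit, procedure or patient is added.

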6.3 Selection of Subjects

Subjects will be enrolled based on the inclusion/exclusion criteria listed in sections 6.3.1 and 6.3.2. The Principal Investigator or a qualified designee will be responsible for confirming that all subjects screened are eligible for the study based on the following inclusion and exclusion criteria:

6.3.1 Inclusion Criteria

1. Scheduled to undergo isolated CABG surgery at a hospital within the UPenn Health System
2. Age ≥18 years
3. Ejection fraction ≥50%
4. Transthoracic echocardiography performed within one year of the CABG surgery
5. Left heart catheterization performed within one year of the CABG surgery
6. English language fluency or facilitated by a language interpreter
7. Able to provide informed consent either in English or via a language interpreter
8. Willing to comply with all study procedures

Clinical Study Number:	NCT06154265	Document Title:	10/24/2024	Page 12 of 36
		Default vs As-Needed Intraoperative Transesophageal Echocardiography (TEE) in Low-Risk Isolated Coronary Artery Bypass Graft (CABG) Surgery: A Randomized Controlled Trial		

6.3.2 Exclusion Criteria

1. Documented valve (aortic, mitral, tricuspid, or pulmonic) disease (stenosis or regurgitation) moderate or greater.
2. Any CABG surgery with either “possible” or “definite” aortic intervention listed as a planned part of the procedure.
3. Any CABG surgery with either “possible” or “definite” valve repair/replacement listed as a planned part of the procedure.
4. Having undergone any previous cardiac surgeries (i.e. scheduled with a “REDO” modifier).
5. Proximal/critical left main coronary disease (e.g. $\geq 90\%$ stenosis).
6. Preexisting anomalous coronary arteries
7. Preexisting end-stage renal disease on hemodialysis
8. Preexisting chronic kidney disease (CKD) stage 3, 4, or 5
9. Stroke with residual focal neurological deficits within 90 days of surgery
10. Any of the following presurgical, mechanical circulatory support devices:
 - a. Intraaortic balloon pump
 - b. Percutaneous right ventricular assist device (RVAD)
 - c. Impella
 - d. Extracorporeal membrane oxygenation (ECMO)
11. Absolute contraindication to echocardiography defined as one or more of the following documented conditions:
 - a. Esophagectomy
 - b. Esophagogastrectomy
 - c. Esophageal trauma
12. Any of these three relative contraindications to TEE:
 - a. Esophageal varices
 - b. Gastric bypass surgery
 - c. Descending thoracic aortic aneurysm
 - d. Oropharyngeal anatomical abnormalities
13. Severe pulmonary hypertension defined as:
 - a. Pulmonary arterial pressure ≥ 60 mmHg
 - b. Pulmonary vascular resistance (PVR) ≥ 3 Woods Units
14. Hemodynamic instability after induction and following placement of an endotracheal tube will be defined as one or more of the following events or scenarios:
 - a. Placement of an intraaortic balloon pump (IABP)
 - b. Initiation of venoarterial extracorporeal membrane oxygenation (VAECMO)
 - c. Placement of a right or left percutaneous mechanical circulatory support device.
 - d. Initiation of epinephrine infusion at a dose ≥ 0.08 mcg/kg/min (i.e. exceeding 4 – 6 mcg/min) for a duration ≥ 5 minutes

Clinical Study Number:	NCT06154265	Document Title:	10/24/2024	Page 13 of 36
		Default vs As-Needed Intraoperative Transesophageal Echocardiography (TEE) in Low-Risk Isolated Coronary Artery Bypass Graft (CABG) Surgery: A Randomized Controlled Trial		

- e. Initiation of norepinephrine at a dose ≥ 0.10 mcg/kg/min (i.e. exceeding 6 mcg/min) for a duration ≥ 5 minutes
- f. Initiation of phenylephrine infusion at a dose ≥ 1.5 mcg/kg/min (i.e. exceeding 100 mcg/min) for a duration \geq minutes
- g. Initiation of vasopressin infusion at a dose ≥ 0.04 units/min for a duration ≥ 5 minutes

7 Withdrawal of Subjects

Study participation is voluntary. Subjects may refuse to consent or withdraw from the study at any time without penalty or loss of benefits.

8 Overview of RCT

This study will be a prospective, parallel design, randomized controlled trial.

8.1 Detailed Study Protocol

- Overview of protocol phases (listed in sequence)

8.2 Screening

- The cardiac surgery outpatient office will serve as the primary location for pre-screening potentially eligible participants but inpatients who meet inclusion criteria will also be eligible. Screening of the clinic schedule or the inpatient cardiac surgical census will identify potential patient subjects that meet study entry criteria. Eligible patients will be approached after it is determined that CABG is indicated for standard of care. Patients will not be approached for enrollment on the day of surgery to allow adequate time for the patient to consider the risks and benefits to participation.
- Patient subjects will be invited to participate in trial at after completing their pre-operative surgical office visit at a UPenn cardiac surgery clinic or following admission to the hospital. Time allotted for patient subject enrollment in the study will be approximately 30-45 minutes in order to adequately allow for a comprehensive discussion on the risks/benefits to patient participation, and to answer any questions that might arise during the consenting process. If English is not the subject's first language an interpreter will be used to facilitate the informed consent process in the subject's native language. The subject will be provided the cellphone number of the PI or their designee and informed that they can call the PI or designee with any questions.

8.3.1 Informed Consent Process

- Study participation is voluntary. Potential subjects, and/or their legal representatives, are given the most current IRB/EC-approved consent

Clinical Study Number:	NCT06154265	Document Title:	10/24/2024	Page 14 of 36
		Default vs As-Needed Intraoperative Transesophageal Echocardiography (TEE) in Low-Risk Isolated Coronary Artery Bypass Graft (CABG) Surgery: A Randomized Controlled Trial		

form to read. If English is not the subject’s first language, a short document in their native language will be provided. They will be provided ample time for review and an opportunity to ask questions about the study. If they agree to participate, they will sign the consent form and be given a copy of the signed document for their records. The original signed copy of the consent form(s) will be retained by the Principal Investigator. Each of these actions/steps will be documented. Only after Informed Consent has been obtained, may the study procedures begin. Informed Consent may also be documented through a 21 CFR Part 11 compliant eConsent tool.

8.3.2 Inability to Provide Consent

- For this study, eligible subjects must be willing and physically able to undergo all study procedures. If they are unable to provide consent, they may not participate.
- Enrollment shall proceed via a signed written Informed Consent by each subject. No study activities will be allowed without prior written consent of the subject. Subjects meeting the eligibility criteria shall be consented and enrolled by the Principal Investigator or CRC delegate. Informed Consent may also be documented through RedCap, a compliant web platform for managing data. Study participation is voluntary. Subjects may refuse to consent or withdraw from the study at any time without penalty or loss of benefits. All steps will be completed in one-day, and subject will be dismissed from the study.

8.3.3 Financial Compensation for Trial Participation

- Patients will not be financially compensated for participation in this trial.

8.3.4 Records of Informed Consent

- Copies of the informed consent document will be provided to all patients participating in the trial.
- It will be reiterated that subjects may elect to de-enroll from the trial at any time.

8.3 Randomization and Trial Protocol

8.4.1 Randomization

- Randomization will occur on the day of surgery after placement of an arterial line for invasive hemodynamic monitoring (routine for all patients undergoing isolated CABG surgery) and following induction of anesthesia and successful placement of the endotracheal tube. This will ensure that any patient who is hemodynamically unstable (defined by the exclusion criteria listed above) following induction of anesthesia is excluded from the trial (and will receive an obligatory intraoperative TEE).

Clinical Study Number:	NCT06154265	Document Title:	10/24/2024	Page 15 of 36
		Default vs As-Needed Intraoperative Transesophageal Echocardiography (TEE) in Low-Risk Isolated Coronary Artery Bypass Graft (CABG) Surgery: A Randomized Controlled Trial		

8.4.2 Trial Protocol for Default (i.e., Obligatory) TEE: Control Arm

- After induction, patients randomized to the default TEE trial arm will have the TEE probe passed into the esophagus after the endotracheal tube has been secured.
- The protocol for those enrolled in the default TEE trial arm will have one pre-surgical TEE exam (defined as ≥ 10 video acquisitions) and one post-surgical TEE exam (defined as ≥ 10 video acquisitions).
- While use (or lack of use) of TEE during isolated CABG surgery are both considered standard-of-care by national guideline recommendations, at the University of Pennsylvania, the typical practice is to place the TEE as a default monitor (i.e., immediately following induction of anesthesia and placement of the endotracheal tube). Therefore, for this pilot trial, this trial arm – the default/obligatory TEE – will be considered the control.

8.4.3 Trial Protocol for As-Needed (i.e. Backup) TEE: Intervention Arm

- After induction of anesthesia, patients randomized to the as-needed TEE trial arm will not have the TEE probe placed after the endotracheal tube has been secured. However, both the TEE machine and TEE probe will both be present in the operating room to minimize any delay in probe placement if TEE is requested by the cardiac surgeon or deemed medically necessary by the cardiac anesthesiologist.
- As described above, because the typical practice at University of Pennsylvania is the obligatory placement of the TEE. Therefore, for this pilot trial, this trial arm – the as-needed/backup TEE – will be considered the intervention arm.

8.4 Data Collection

8.5.1 Electronic Medical Record (EMR) Data Collection

- The PI ([name]) or other IRB-approved research personnel will collect post-surgical, clinical information from the electronic medical record, pre-surgically, and up to 5 days post-surgery. All data will be collected and securely stored on RedCap or on a single, password-protected, UPenn-regulated, laptop owned by the PI ([name]). No paper records will be kept.

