Secondary Objectives	
Secondary Objectives:
 
 1. Evidence of clinically-significant gastroesophageal dysfunction during hospitalization – either by patient-reported symptoms or by the presence of testing for swallowing difficulty, dysfunction, or upper endoscopy diagnostic procedures. 2. Evidence of end-organ dysfunction based on clinical notes (e.g. “transaminitis,” “acute kidney/renal injury”), and/or laboratory-based evidence of (e.g. liver function tests [LFTs], serum creatinine [Cr], lactate, etc.). 3. Incidence of in-hospital, post-surgical, cardiovascular re-intervention (e.g. return to the operating room for any reason, unplanned or emergency cardiac catheterization post-surgery, or placement on venoarterial extracorporeal membrane oxygenation [VAECMO]). 4. Incidence of all-cause in-hospital mortality
Population	Isolated CABG surgery patients meeting trial eligibility criteria (see inclusion/exclusion), scheduled to undergo surgery at hospitals within the University of Pennsylvania Health System.
Key Eligibility Criteria	In addition to meeting strict inclusion and exclusion criteria, subjects must be willing and capable of providing informed consent and physically capable of performing study related activities.
Site	Hospitals within the University of Pennsylvania Health System

Clinical Study Number:	NCT06154265	Document Title:	10/24/2024	Page 7 of 36
		Default vs As-Needed Intraoperative Transesophageal Echocardiography (TEE) in Low-Risk Isolated Coronary Artery Bypass Graft (CABG) Surgery: A Randomized Controlled Trial		

Study Duration	24 months
Participant Duration	
Active participations: Informed consent duration: approximately 30 – 60 minutes
 
Study duration: 5 days (120 hours) starting with the time of patient enters the cardiac operating room for CABG surgery.
 
Passive participation: Full study duration for the purposes of data acquisition, data cleaning, report generation, manuscript preparation and publication where applicable.
 
Total time: ~24 months

Clinical Study Number:	NCT06154265	Document Title:	10/24/2024	Page 8 of 36
		Default vs As-Needed Intraoperative Transesophageal Echocardiography (TEE) in Low-Risk Isolated Coronary Artery Bypass Graft (CABG) Surgery: A Randomized Controlled Trial		

4 Background Information

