10.2 Secondary Endpoint Analysis

Although this study is not powered to detect a difference in clinical outcomes between the default and as-needed intraoperative TEE groups, to plan for a future RCT that would be powered to detect a difference in clinical outcomes. We will collect clinical data on gastroesophageal dysfunction (symptoms or injury), incidence of end-organ dysfunction, and incidence of death as defined by the following:

1. Evidence of clinically-significant gastroesophageal dysfunction during hospitalization – either by patient-reported symptoms or by the presence of testing for swallowing difficulty, dysfunction, or upper endoscopy diagnostic procedures.
2. Evidence of end-organ dysfunction based on clinical notes (e.g. “transaminitis,” “acute kidney/renal injury”), and/or laboratory-based evidence of (e.g. liver function tests [LFTs], serum creatinine [Cr], lactate, etc.).
3. Incidence of in-hospital, post-surgical, cardiovascular re-intervention (e.g. return to the operating room for any reason, unplanned or emergency cardiac catheterization post-surgery, or placement on venoarterial extracorporeal membrane oxygenation [VAECMO]).
4. Incidence of all-cause in-hospital mortality

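### Three secondary endpoints run over the hospital stay, but record collection is set to stop 5 days after surgery, and the plan does not say how later events are captured or classified

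*Combined protocol and SAP*

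**What the plan says.** Section 10.2, repeated in the synopsis (section 3), lists four secondary endpoints. Three have a hospital-stay window: "Evidence of clinically-significant gastroesophageal dysfunction during hospitalization", "Incidence of in-hospital, post-surgical, cardiovascular re-intervention" and "Incidence of all-cause in-hospital mortality". The remaining one, "Evidence of end-organ dysfunction based on clinical notes" or laboratory values, has no window.

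On collection, section 8.5.1 states that the investigator or approved research personnel "will collect post-surgical, clinical information from the electronic medical record, pre-surgically, and up to 5 days post-surgery". Section 8.5.2 places the interviews in the same period: "the second interview will occur at any point between 1 – 5 days post-surgery".

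The synopsis describes participation in two parts. Under active participation it gives "Study duration: 5 days (120 hours) starting with the time of patient enters the cardiac operating room for CABG surgery". Under passive participation it gives "Full study duration for the purposes of data acquisition, data cleaning, report generation, manuscript preparation and publication where applicable", for a total of about 24 months.

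Adverse events are a separate route. Sections 8.6 and 13.1 run their collection from consent until study-related activities end, with no day attached. Section 19.1.1.2 says they are found by patient report or by scheduled record reviews, without giving the schedule.

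**The concern.** An endpoint defined to discharge needs collection to discharge. If staff follow section 8.5.1 as written, they obtain 5-day outcomes and report them under an in-hospital label. Nothing in the plan tells them what to enter for a patient who is still in hospital when collection stops.

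Section 10.2 says the clinical data are gathered to help plan a later trial powered for clinical outcomes. A rate that is silently cut at day 5 would be carried into that planning as if it covered the whole stay, and it could not be compared fairly with in-hospital rates from other sources.

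**Working it through.** **No plan figure to reproduce.** Section 19.5.2 says no formal power calculation was done, and the documents give no length of stay and no timing of events. The only arithmetic in the text, 5 days × 24 = 120 hours, agrees with itself. The check is therefore a comparison of windows, followed by an illustration of size.

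**Windows side by side**

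| Item | Endpoint window | Stated collection window |
|---|---|---|
| Gastroesophageal dysfunction, record-based part | Hospital stay | To day 5 (8.5.1) |
| Gastroesophageal dysfunction, patient-reported part | Hospital stay | Interviews to day 5 (8.5.2) |
| Cardiovascular re-intervention | Hospital stay | To day 5 (8.5.1) |
| All-cause mortality | Hospital stay | To day 5 (8.5.1) |
| End-organ dysfunction | None stated | To day 5 (8.5.1) |

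For a patient discharged by day 5 the record covers the whole stay. For a patient in hospital on day 6 or later the two windows separate.

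**Could another route close the gap?**

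- Passive participation: the synopsis names data acquisition as a purpose, but does not say which data are acquired after day 5 or that this overrides section 8.5.1.
- Adverse events: the list in section 19.1.1.1 includes death, unplanned percutaneous intervention, bypass revision, re-operation for bleeding, gastrointestinal or esophageal complications that need testing, and failed swallow evaluation. The re-intervention endpoint counts a return to the operating room for any cause, and also VA-ECMO. The list does not itemise VA-ECMO and has no general entry for non-bleeding returns. No section says that adverse event records feed the endpoint counts.
- Analysis: section 19.5.1 names intention-to-treat, chi-squared and Wilcoxon rank-sum, with no rule for censoring, missing data or a fixed horizon.

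**Illustration of size.** Inputs:

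- N = 44 (22 per arm, section 10.3) or N = 22 (section 19.5.2). The documents conflict, so both are shown.
- p, the true in-hospital event rate, is assumed. The 4% value is the top of the 0.1%–4% range for gastroesophageal injury in sections 4 and 11.1, which is not the rate of any endpoint as defined here.
- f, the share of events after day 5 that go uncaptured, is assumed at 10%, 25% or 50%.

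Formulas: observed rate = p(1−f); expected missed events = N·p·f; chance of at least one missed = 1−(1−pf)^N. Example with N = 44, p = 4%, f = 25%: observed rate 0.04 × 0.75 = 3.0%; missed 44 × 0.04 × 0.25 = 0.44; chance 1−0.99^44 = 36%.

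| p | f | Observed rate | Missed, N = 44 (chance of ≥1) | Missed, N = 22 (chance of ≥1) |
|---|---|---|---|---|
| 1% | 10% | 0.90% | 0.04 (4%) | 0.02 (2%) |
| 1% | 25% | 0.75% | 0.11 (10%) | 0.06 (5%) |
| 1% | 50% | 0.50% | 0.22 (20%) | 0.11 (10%) |
| 4% | 10% | 3.6% | 0.18 (16%) | 0.09 (8%) |
| 4% | 25% | 3.0% | 0.44 (36%) | 0.22 (20%) |
| 4% | 50% | 2.0% | 0.88 (59%) | 0.44 (36%) |
| 10% | 10% | 9.0% | 0.44 (36%) | 0.22 (20%) |
| 10% | 25% | 7.5% | 1.10 (67%) | 0.55 (43%) |
| 10% | 50% | 5.0% | 2.20 (90%) | 1.10 (68%) |

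The count lost in this trial is small in most rows. The relative understatement equals f whatever the sample size.

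**The case against.** The strongest reply is that the plan never says late events are lost. A reader might infer that a patient with an event on day 6 is entered as event-free. With proportions compared by chi-squared and no missing-data rule that would be a natural default, but no section states it. Passive data acquisition and adverse event review could pick up a late death, a bleeding re-operation or a gastrointestinal work-up. This stands as far as it goes: loss is possible, not established. It does not remove the conflict, because neither route is tied to the endpoints and neither has a defined end.

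Two further inferences lack support. A reader might take the 120 hours as a second and tighter limit on record review, but it sits under active participation. A reader might also say that the events at risk belong to the sickest patients. Some listed complications, such as prolonged intubation or pneumonia, could plausibly lengthen a stay, but the documents give no length-of-stay data, so informative truncation is plausible and not shown.

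It can also be said that the effect is minor beside sampling error. That is fair for this trial's own estimates: zero events in 44 patients has a two-sided 95% upper limit of 1−0.025^(1/44) = 8.0%, and in 22 patients 1−0.025^(1/22) = 15.4%. But sampling error is visible in a confidence interval, whereas a mislabelled window is not, and more patients would not cure it.

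**Conclusion.** The mismatch is in the text and needs no assumption: three endpoints extend to discharge, record collection is set to end at day 5, and the handling of anyone between the two is unspecified. Rates reported as in-hospital could be 5-day rates and could be too low for planning the future trial.

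How much too low cannot be derived from the documents. The factor (1−f) assumes that late events are missed altogether, and each value of p and f in the illustration is an assumption, not an estimate for this trial.

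Severity is moderate. The affected endpoints are secondary and expressly unpowered. Recruitment and TEE use in the as-needed arm do not depend on this window, so a reader should not infer that the feasibility conclusions are at risk.

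**What to change.** Use one window throughout.

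- In section 8.5.1 and the synopsis, state that outcomes are collected from the medical record through discharge from the index admission.
- Give end-organ dysfunction the same record-based window.
- State that the patient-reported part of the gastroesophageal endpoint is assessed only to day 5, and report it separately from the record-based part, so that one composite does not carry two windows.
- Define in sections 8.6, 13.1 and 19.1 when adverse event and serious adverse event capture ends, to match, and say whether those records contribute to the endpoint counts.
- If collection must stop at day 5, rename the three endpoints as 5-day outcomes, give end-organ dysfunction the same limit, and say that events after day 5 are outside the definition.

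The cost is a few minutes more chart review per patient and a short amendment to the protocol, with the consent form changed to match if it states the collection period. The renaming option needs only the amendment.
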